Pesticides: Dust samples will be collected by wiping a measured 12-inch square section of the floor along the baseboard in the kitchens. Samples will be gathered on gauze squares wetted with isopropanol and will be analyzed using gas chromatograph/mass spectrometry (GC/MS) and HPLC (High-performance liquid chromatography/ mass spectrometry (Table 5). Common pyrethroid (*cis* and *trans* permethrin, cyfluthrin), organophosphate, and carbamate pesticides will be analyzed in addition to a synergist that is used uniquely in pyrethroid pesticides (piperonyl butoxide).

Table 5. A list of pesticides that EPA can measure in environmental samples.

Organochlorines	Pyrethroids/Pyrethrins
α- and γ- Chlordane	Allerthrin
Heptachlor	Bifenthrin
P,p=DDT	Cyfluthrin I, II/III, IV
P,p=DDE	Cypermethrin I, II/III, IV
Organophosphates	Deltamethrin
Chlorpyrifos	Esfenvalerate
Diazinon	Fenpropathrin
Malathion	Imiprothrin
Phenyl-Pyrazole	Λ-cyhalothrin
Fipronil	Cis - and trans -Permethrin
Other	Pyrethrin I, II
Piperonyl Butoxide	Prallethrin
	Resmethrin
	Sumithrin
	Tetramethrin I, II

Air Exchange Rates (AER): Air exchange rates can be quantified using non-toxic tracer gases such as SF₆ and perfluorinated methylcyclohexane (PMCH). The method to be employed in this study will use the perfluorocarbon, PMCH. In brief, the method is accomplished using by releasing the tracer gas inside the home and allowing it to reach steady state. With passive air sampling for a period of 12 hours up to one week, the PMCH is collected and then analyzed by gas chromatography and electron capture detector (GC/ECD). The

[figure not shown]
range of quantification is 0.10 to 2.5 air changes per hour (ACH), and the upper limit of detection is about 3.0 ACH.

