Sample size overviews: The most complete data to obtain sample size estimates for our proposed study are derived primarily from studies of allergens and asthma. Based upon our calculations, we estimate that we will need at least 13 green buildings and 13 control buildings with at least 25 apartments in each building for a total $n = 650$ to detect differences in environmental exposures (notably allergens). In addition, we need at least 548 asthmatic children ($n=274$ in green and $n= 274$ in control buildings) to detect differences in asthma symptom days. With an anticipated loss to follow-up over a 1-year period = 20%, we will need at least 688 children with asthma (7-12 years) and 814 homes to assess exposure differences. We will enroll the children from 832 homes in order to ensure adequate power to detect both the asthma and exposure outcomes for the 13 study sites (i.e., 64 homes in each study site). The details of our sample size calculations are listed below and the equations that were used were from a book on longitudinal data analysis by Diggle, Liang, and Zeger (1994).

Sample size calculations for the overall difference between environmental exposures in green vs. control homes can be given as a simple test of two proportions and means; however a specific difficulty arises when trying to adjust for temporal and spatial correlations between measurements. A study that had enough measurements to assess spatial and temporal correlation was an integrated pest management (IPM) study conducted in New York

City (Chew et al. 2006; Kass et al. 2009). We have used the design effect from this study to estimate the number of clusters (or buildings) needed to detect differences in cockroach allergen because IPM is also one of the main green characteristics in the Green Housing Study. Assumptions from the aforementioned study comparing IPM to non-IPM homes are listed below:

- 1 13 buildings
 - 2 About half were treatment and the other half control
 - 3 3 repeated measures at: baseline (before IPM), 3months later (post-IPM), and 6months later (post-IPM)
 - 4 On average, 25 apartments within each building were measured
 - 5 For the control homes, the correlations between baseline and 3-month follow-up cockroach allergen measurements and 3-month and 6 months follow-up measurements were approximately equal to 0.5.
- Design effect due to clustering = 3.62

Equation 1. Sample size for repeated measures – cockroach allergen.

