$$m = D * [2(z_{\alpha} + z_{\rho})^2 \{1 + (n - 1)\rho\}] / (n\Delta^2)$$

m = number in each group (e.g., intervention and non-intervention)

n = number of repeated measurements (equals 3 in this scenario)

z_{α} = Z score for alpha = 0.05

z_{ρ} = Power, set at 0.80

ρ = correlation among repeated observations

$\Delta = d / \sigma$ where d is the smallest meaningful difference and σ is the standard deviation

D = Design effect due to clustering (This was not in the formula used by Diggle et al., but was added to adjust for clustering expected in our study)

Note: we also assumed a design effect (e.g., increase (multiplicative) sample needed because of the effects of clustering) equal to 3.62. This is the ratio in clustering sampling variance divided by the simple random variance (of the same size) (i.e., the denominator without clustering taken into account).

When calculating the sample sizes, we used two standardized effect sizes based on the IPM study: 0.37 and 0.30. The effect size of 0.37 is based on the ability to detect a difference of 0.8148 ln units of the *Blatella germanica* cockroach allergen (i.e., Bla g 2) and a standard deviation of ~ 2.2. The effect size of 0.30 is based on the ability to detect a difference of 0.649 ln units of Bla g 2 and a standard deviation of 2.2. We also assumed an alpha of 0.05 and a power of 80%). The sample size based on changing the expected correlation between repeated measures would result is presented in Table 8.

Assuming a correlation of 0.5 we get the following:

- 1 With assumption 1, we would need 16 buildings (8 green and 8 control) with at least 25 apartments per building
- 2 With assumption 2, we would need 26 buildings (13 green and 13 control) with at least 25 apartments per building.

Table 8. Sample size requirements for number of buildings.

Correlation between repeated measures	Sample size requirements (number of buildings)	
	Assuming Delta=0.377	Assuming Delta=0.30
0.2	6	9
0.3	7	11

0.4	8	12
0.5	8	13
0.6	9	15
0.7	10	16
0.8	11	17

*samples size is for each group (e.g., 8 buildings means 8 control and 8 green buildings)

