We also estimated the sample size for detecting differences in pesticides and VOCs. To date, there is only one study of an intervention to decrease pesticide exposures that used objective measurements of pesticide levels in residential homes in a non-agricultural environment (Williams et al). This study was conducted in homes of Latina and African-American women living in low-income housing in New York. In the study, 25 homes underwent IPM as an intervention. The pesticide synergist, piperonyl butoxide, is unique to pyrethroid pesticides and this was an analyte that was measured in the study's air samples. We used their pre- and post piperonyl butoxide concentrations (pre = mean $1.66 \pm \text{s.e. } 0.71 \text{ ng/m}^3$ vs. post = mean $0.8 \pm \text{s.e. } 0.22 \text{ ng/m}^3$) for our calculations of sample size which are shown in Table 9.

To date, there is only one study comparing the VOC levels in newly-built green homes and conventionally-built homes; therefore, this was not a renovation like our proposed study. We calculated the sample size based on their measurements of formaldehyde in the two types of homes in their study. This study was conducted in Finland. In the study, 6 apartments in each type of building had air measurements for formaldehyde (green-built: mean = $13 \mu\text{g/m}^3$, s.d. = 4 vs. conventionally-built: mean $23 \mu\text{g/m}^3$, s.d. = 5). We calculated the sample size necessary to detect a decrease in 50%, 25%, and 15%, of the difference in formaldehyde levels observed in their two study groups (see Table 9).

Devos et al (1990) have suggested that the minimum level of an indoor irritant be set with a safety factor of 40 (Devos, Patte et al. 1990). Given that the American Conference of Governmental Industrial Hygienists (ACGIH) threshold limit value is $368 \mu\text{g/m}^3$, a minimum level of formaldehyde below which no irritant effects are expected is $9.8 \mu\text{g/m}^3$ (which is the CDC/ATSDR Minimum Risk Level, <http://www.atsdr.cdc.gov/ToxProfiles/tp.asp?id=220&tid=39>). Based upon Table 9, we believe that detecting differences of $9.8 \mu\text{g/m}^3$ should not be a problem with at least 37 homes in each study group.

Table 9. Calculations of samples sizes for VOCs and pesticides

Analyte	Design Effect	Effect Size (Δ)	Required Sample size (in each group)
Formaldehyde			
- 15% : $1.5 \mu\text{g/m}^3$	3.6	0.33	408
- 25% : $3.5 \mu\text{g/m}^3$	3.6	0.77	75
- 50% : $5 \mu\text{g/m}^3$	3.6	1.10	37

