(based on Tuomainen et al, 2003)			
Piperonyl butoxide			
0.8 ng/m^3 decrease	3.6	0.33	418
(based on Williams et al, 2006)			

* $\alpha = 0.05$, $1-\beta = 0.80$

Summary of samples size for environmental exposures: Of the intervention studies relevant to green housing, the sample size calculations based upon the cockroach allergen intervention study provided the most information to inform our estimates of sample size required for the Green Housing Study. Because [name] was a co-author on the manuscript and had analyzed the cockroach allergen samples in her laboratory, she had

access to the repeated measurements database and this helped to guide our design effect due to clustering of apartments within buildings. The other papers did not have repeated measurements (thus the variance estimates were rather wide) and they also had more restrictive groups (e.g., nonsmoking pregnant women, Finnish families living in newly-constructed apartments) than is planned in the Green Housing Study. Thus, we believe that our conservative estimate to recruit residents in 64 apartments in each of 13 cities (total n= 832 homes) to account for potential loss-to-follow-up, should ensure adequate sample size for assessing differences in exposure levels.

Sample size for assessing asthma outcomes: The calculation for assessing differences in health markers were based upon a multi-site asthma intervention study (Morgan et al. 2004). In this study, 407 asthmatic children with the multi-factorial intervention (asthma trigger education, mattress covers, IPM, HEPA filter units) had fewer days (2.62 days ± 0.12) than those (n=414) without the intervention (3.21 days ± 0.13). Table 10 shows sample sizes with different assumptions of effect sizes using equation 2.

Equation 2. Sample size for asthma morbidity outcomes.

$$m = D * [2(z_{\alpha} + z_{\beta})^2 \{1 + (n - 1)\rho\}] / (n\Delta^2)$$

m = number in each group (e.g., intervention and non-intervention)

n = 1 (note: for differences of differences, we assumed a value of 1)

z_{α} = Z score for alpha = 0.05

z_{β} = Power, set at 0.80

ρ = correlation among repeated observations

Δ = d/ σ where d is the smallest meaningful difference and σ is the standard deviation

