of indicator variables for the presence or absence of certain allergens or combinations of allergens. Allergen concentrations will be reported as μg of allergen per g of collected dust and μg of allergen per unit area vacuumed.

VOCs and pesticides in the homes: Variables related to VOCs (whether total or speciated) and pesticides (pyrethroids, propoxur, and piperonyl butoxide) in the homes may take the form of continuous measures or indicator variables for the presence or absence of certain chemicals or combinations of chemicals. Concentrations will be reported as ppm (and also $\mu\text{g}/\text{m}^3$) in the case of the VOCs and $\mu\text{g}/\text{g}$ in the case of the pesticides.

Conditions of the home environments: Factors that may influence the presence and levels of allergens, VOCs, and pesticides include: the presence of carpets; pests; housing type and age, average winter temperature and relative humidity, air exchange rates.

Wheeze /asthma severity: This information may be used in the form of categorical and continuous variables (number of emergency room visits for asthma, use of asthma medications, lost school days). Nights awakened by asthma, and spirometry measurement such as FEV1 and FEF_{25-75%}).

Additional environmental and host factors for disposition to wheeze/asthma: Other risk factors for the main outcomes of interest include: environmental tobacco smoke; acute respiratory illnesses; gender; socioeconomic status of primary caregiver; degree of acculturation (operationalized); and deficiencies in access to and quality of health care. Many of these factors allow for a variety of formulations. Environmental tobacco smoke, for example, may be analyzed as an indicator variable for the presence or absence of smoking in the home, as count data for the number of smokers in the home, or as a continuous variable for the number of cigarettes smoked per day in the home. The choice of formulation of risk factors will be driven by the aim of clarifying the main relationships of interest, for example the role of allergens in the development of early allergic sensitization and asthmatic airways disorders.

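### The claim that 832 homes suffice for exposure differences is contradicted by Table 9's only pesticide row (418 per group needed, about 333 expected to remain), and its 25% formaldehyde row uses the wrong difference

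*Protocol*

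**What the plan says.** All places are in the Protocol, section IV (Methods).

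- **Design.** The Overview plans 32 green and 32 control homes at each of 13 sites, 832 in total.
- **Loss.** Sample size overviews states: "With an anticipated loss to follow-up over a 1-year period = 20" (per cent).
- **Adequacy.** The summary of sample size for environmental exposures says the 832 homes "should ensure adequate sample size for assessing differences in exposure levels". Sample size overviews and the summary for asthma outcomes repeat that 832 homes give adequate power for exposures.
- **Formaldehyde.** The text above Table 9 says: "We calculated the sample size necessary to detect a decrease in 50%, 25%, and 15%, of the difference in formaldehyde levels observed" in the source study, whose means are 13 (SD 4) and 23 (SD 5) µg/m³. Table 9 enters 1.5, 3.5 and 5 µg/m³, needing 408, 75 and 37 per group.
- **Pesticides.** The source is a study of 25 homes with piperonyl butoxide at 1.66 (SE 0.71) before and 0.8 (SE 0.22) ng/m³ after the intervention; "this was an analyte that was measured in the study's air samples". Table 9 labels the row a 0.8 ng/m³ decrease and requires 418 per group.
- **Measurement.** In this trial, "Dust samples will be collected by wiping a measured 12-inch square section of the floor along the baseboard in the kitchens". Main Variable Definitions gives µg/g as the unit "in the case of the pesticides", and Descriptive statistics plans log transformation of pesticide levels.

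**The concern.** The adequacy sentence covers exposure differences in general, yet the one calculation offered for a pesticide asks for more homes per group than are enrolled, before any loss. Pesticides are not peripheral: Hypothesis 1.a predicts lower concentrations in green homes, and the section on regression models lists pesticide levels among the main outcomes. A null pesticide result from a study declared adequately sized could be read as evidence of no difference. The formaldehyde slip is separate: one of three rows does not follow the rule stated for all three.

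**Working it through.** **Formula.** Equation 1 with one measurement (n = 1): m = D × 2 × (z_α + z_power)² / Δ², where Δ is the difference divided by the SD. The protocol lists "Z score for alpha = 0.05" and "Power, set at 0.80" without stating sidedness. D is 3.62 in the text and 3.6 in Table 9.

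One-sided: (1.645 + 0.842)² = 6.183, and 2 × 3.62 × 6.183 = 44.76.
Two-sided: (1.960 + 0.842)² = 7.849, and 2 × 3.62 × 7.849 = 56.83.

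**Formaldehyde, reproducing the table.** Pooled SD = √((4² + 5²)/2) = 4.528.

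| Difference (µg/m³) | Δ | One-sided | Two-sided | Table 9 |
|---|---|---|---|---|
| 1.5 | 0.331 | 407.8 | 517.7 | 408 |
| 3.5 | 0.773 | 74.9 | 95.1 | 75 |
| 5 | 1.104 | 36.7 | 46.6 | 37 |

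**Piperonyl butoxide, reproducing the table.** SDs from the SEs with 25 homes: 0.71 × 5 = 3.55 and 0.22 × 5 = 1.10. Pooled SD = √((3.55² + 1.10²)/2) = 2.628. Difference = 1.66 − 0.8 = 0.86, so Δ = 0.86/2.628 = 0.327.
m = 44.76/0.327² = 418.0 one-sided, matching the table; 530.6 two-sided. The labelled 0.8 would need 483 one-sided, so 418 comes from 0.86. Table 9 therefore reproduces only with one-sided alpha.

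**Homes available.** 832/2 = 416 per group; 416 × 0.8 = 332.8 retained. Shortfall: 418 − 333 = 85 per group.

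**Power at 332.8 per group, piperonyl butoxide, one measurement.** √(332.8 × 0.327²/(2 × 3.62)) = 2.219 (unrounded Δ).
- One-sided: Φ(2.219 − 1.645) = 0.717.
- Two-sided: Φ(2.219 − 1.960) = 0.602.

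At the full 416, power is about 80% one-sided and 70% two-sided.

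**Credit for repeated visits.** Equation 1 with n = 3 multiplies m by (1 + 2ρ)/3. The protocol gives ρ = 0.5 for cockroach allergen only, so a range is assumed for pesticides.

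| ρ | Needed, one-sided | Needed, two-sided | Power at 333, one-sided | Power at 333, two-sided |
|---|---|---|---|---|
| 0.2 | 195 | 248 | 95% | 90% |
| 0.5 | 279 | 354 | 86% | 78% |
| 0.8 | 362 | 460 | 77% | 66% |

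**The 25% formaldehyde row.** Observed difference 23 − 13 = 10; 50% is 5 and 15% is 1.5, as tabulated. 25% is 2.5, but 3.5 (35%) was entered. Δ = 2.5/4.528 = 0.552; m = 44.76/0.552² = 146.8, i.e. 147 (186.4, i.e. 187, two-sided). The tabulated effect size and sample size both follow from 3.5, so the wrong difference entered the calculation.

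**Cockroach allergen, for comparison.** Δ = 0.30, n = 3, ρ = 0.5: 44.76 × (2/3)/0.09 = 332 per group one-sided (13.3 buildings of 25; Table 8 prints 13); 56.83 × (2/3)/0.09 = 421 two-sided. This sizing also matches only one-sided.

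**The case against.** The strongest defence is that the protocol gives Table 9 less weight. It says the cockroach study was the most informative source, and that the others lacked repeated measurements, had wide variance estimates and studied narrower groups. The trial visits each home four times and compares it with its own baseline, so a single-measurement requirement overstates the need. This stands in part: with n = 3 and ρ = 0.5, 333 per group is enough one-sided, though not two-sided. But the protocol makes no such calculation for pesticides, and doubting the inputs does not show that the size is adequate.

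The excess of 418 over 416 enrolled is also fragile: with D = 3.6, as printed in Table 9, the requirement is 415.7. The gap that matters is to the 333 retained.

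Four stronger readings are tempting and are not supported:

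- A reader might count the 15% formaldehyde row (408) as a second shortfall. It is one of three scenarios. The text relies on the 37-per-group row. VOCs are also measured one week after renovation, before most of the one-year loss would accrue.
- A reader might take 60–72% as the trial's power for pesticides. It is the power on Table 9's single-measurement basis only.
- A reader might conclude that the 25% row leaves formaldehyde underpowered. The corrected 147 (187 two-sided) is far below 333.
- A reader might infer that µg/g cannot be obtained from these wipes. The Pesticides section does not say whether they are weighed, and detailed procedures are left to the Manual of Procedures.

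**Conclusion.** The concern holds in two parts. First, the general adequacy claim conflicts with Table 9's only pesticide row: 418 per group needed, 416 enrolled, about 333 retained. On that row's own basis power is about 72%, or 60% two-sided. With three repeated measurements it would be 77–95% one-sided or 66–90% two-sided as ρ falls from an assumed 0.8 to 0.2. The unqualified claim is therefore unsupported; the documents do not establish that pesticides are underpowered in the repeated-measures design. Second, the 25% formaldehyde row is wrong by the protocol's own definition (75 should be 147), with no effect on whether the sample suffices.

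These results assume equal groups, 20% loss in each, and the source study's SEs converted with 25 homes. The pesticide figures are indicative at best, because they use raw-scale air concentrations while the trial will analyse log-transformed wipe results, for which no SD is given.

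**What to change.** 1. In the exposure summary, and where it is repeated in Sample size overviews and the asthma summary, stop the adequacy statement from covering pesticides without qualification. State the piperonyl butoxide power at about 333 per group on one declared convention: 72% one-sided or 60% two-sided with one measurement; or, with Equation 1 and n = 3, the range above with the assumed ρ stated.
2. State that Tables 8 and 9 rest on one-sided alpha 0.05, and apply the same sidedness to every exposure. If two-sided testing is intended, the cockroach sizing must be restated too (about 421 per group).
3. Correct the 25% formaldehyde row to 2.5 µg/m³, effect size 0.55 and 147 per group (one-sided), or relabel it 35%.
4. Correct the piperonyl butoxide label from 0.8 to 0.86 ng/m³.
5. Note that the piperonyl butoxide row comes from raw-scale air data and is only indicative for log-transformed wipe results. Reconcile the µg/g unit with the measured-area wipe: mass per area wiped, unless dust mass is obtained.

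The cost is edits to text and tables; no added homes, visits or assays.

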From each of these geographically-stratified study sites, 32 green intervention homes and 32 control homes (total = 64 homes * 13 study sites = 832 homes) will be included. Within each study site (i.e., city), both the green intervention and control homes will be from the same housing development or neighborhoods to ensure homogeneity with regard to housing type and other socioeconomic factors. Changes in environmental measurements (pesticides, VOCs, particulate matter (i.e., PM 2.5 and 1.0), indoor allergens, and fungi) over the 1-year follow-up in both types of housing (green intervention and control) will be compared, thus each home's follow-up measurements will be compared with its own baseline exposure level. This two-group pre-post within-group and between-group comparison will increase ability to detect differences in exposure levels and asthma outcomes that might result from the green renovations in our study. In addition, we will compare environmental measurements and health outcome data with national surveillance data (i.e., National Health and Nutrition Examination Survey (NHANES) and the National Lead and Allergen survey) or other relevant populations (e.g., National Cooperative Inner City Asthma Study (NCICAS), Inner City Asthma Study (ICAS)). At this time, these sites have not been determined by HUD and CDC. When the study sites are selected, the data collection partners will include: 1) CDC; 2) HUD, and 3) the contracted research institutions (to be determined).

An overview of the study implementation is described below. Briefly, study sites will be selected, participants will be recruited at each study site, survey, clinical, and environmental sample collection will occur at repeated time points, samples will be analyzed in selected laboratories, statistical analysis will be conducted, and results will be translated to participants and the community in general. All study consent forms and questionnaires will be available in both English and Spanish (by certified translators). Reading level will be maintained at an 8th grade level (Flesh-Kinkaid assessment available through Microsoft Word).

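### The protocol calls 832 homes adequate for exposure outcomes in general, but Table 9 asks for 418 homes per group for its only pesticide row and 408 for its smallest formaldehyde row, against about 333 per group after the planned loss

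*Protocol*

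**What the plan says.** All references are to the protocol, section IV (Methods).

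- **Enrolment (Overview):** from each site, "32 green intervention homes and 32 control homes (total = 64 homes * 13 study sites = 832 homes) will be included".
- **Loss (Sample size overviews):** "With an anticipated loss to follow-up over a 1-year period = 20" per cent. The allergen-based need of 650 homes is inflated to 814, and 832 are to be enrolled.
- **Table 9:** under the column "Required Sample size (in each group"), it gives 408, 75 and 37 for formaldehyde differences of 1.5, 3.5 and 5 µg/m³, and 418 for piperonyl butoxide. The footnote sets alpha at 0.05 and power at 80%.
- **Summary of sample size for environmental exposures:** directly after Table 9, the 832 homes are described as a conservative number that allows for loss and "should ensure adequate sample size for assessing differences in exposure levels". The sentence is not limited to allergens. Sample size overviews and the summary for asthma outcomes repeat, also without limit, that 832 homes secure power for exposure outcomes.
- **Regression models:** allergen, VOC and pesticide levels in the home are all named as main outcomes.

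**The concern.** A table of requirements is followed at once by a statement that the planned size is enough, yet two of the table's four rows exceed the number of homes expected to remain. The 20% inflation is applied to the allergen requirement but not to Table 9.

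Piperonyl butoxide matters most, because it is the only pesticide scenario and no larger-effect row stands beside it. Integrated pest management is a required feature of the green homes, Hypothesis 1 predicts lower pesticide concentrations, and the Atlanta pilot found no pesticide difference between housing types. If this study also finds none, a reader relying on the adequacy statement could take the result as evidence of no effect from a study sized to find one.

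**Working it through.** **Inputs**

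- Homes per group: 32 × 13 = 416. After 20% loss: 416 × 0.8 = 332.8.
- Design effect: the assumptions under Sample size overviews give "Design effect due to clustering = 3.62"; Table 9 prints 3.6.
- Alpha: Equation 1 says only "Z score for alpha = 0.05"; sidedness is not stated.
- Formaldehyde: SDs 4 and 5, so pooled SD = √((16 + 25)/2) = 4.528.
- Piperonyl butoxide: means 1.66 and 0.80, standard errors 0.71 and 0.22, 25 homes. SDs are 0.71 × 5 = 3.55 and 0.22 × 5 = 1.10; pooled SD = √((3.55² + 1.10²)/2) = 2.628.

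**Step 1: reproduce Table 9.** Equation 1 with one measurement per home is m = D × 2(z_α + z_power)²/Δ². With D = 3.62, z_α = 1.645 and z_power = 0.842:

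| Row | Δ | m, one-sided | Printed | m, two-sided |
|---|---|---|---|---|
| Formaldehyde 1.5 | 1.5/4.528 = 0.331 | 407.8 | 408 | 518 |
| Formaldehyde 3.5 | 3.5/4.528 = 0.773 | 74.9 | 75 | 95 |
| Formaldehyde 5 | 5/4.528 = 1.104 | 36.7 | 37 | 47 |
| Piperonyl butoxide | 0.86/2.628 = 0.327 | 418.0 | 418 | 531 |

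All four rows match with one-sided alpha and none with two-sided alpha. The piperonyl butoxide row is labelled 0.8 but matches only with the unrounded difference 1.66 − 0.80 = 0.86; a difference of 0.8 would need 483 per group one-sided.

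**Step 2: compare with retained homes.**

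- 418 > 332.8 and 408 > 332.8: not met.
- 75 and 37 < 332.8: met, two-sided as well.
- Cockroach allergen (effect 0.30, three measurements, correlation 0.5): 13 × 25 = 325 per group as stated, or 331.6 from Equation 1 one-sided. Both are below 332.8: met.

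Retaining 408 and 418 homes per group after 20% loss would mean enrolling 408/0.8 = 510 and 418/0.8 = 522.5, so 523.

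**Step 3: power at 332.8 per group.** Power = Φ(Δ/√(2D/m) − z_α), with √(7.24/332.8) = 0.1475.

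| Row | One-sided | Two-sided |
|---|---|---|
| Formaldehyde 1.5 | Φ(2.246 − 1.645) = 0.73 | Φ(2.246 − 1.960) = 0.61 |
| Piperonyl butoxide | Φ(2.219 − 1.645) = 0.72 | Φ(2.219 − 1.960) = 0.60 |

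The difference detectable with 80% power is (1.645 + 0.842) × 0.1475 = 0.37 SD one-sided, or (1.960 + 0.842) × 0.1475 = 0.41 SD two-sided.

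**Step 4: effect of repeated visits.** Equation 1 with n = 3 and ρ = 0.5, the values used for cockroach allergen, multiplies the need by (1 + 2 × 0.5)/3 = 2/3. The formaldehyde 1.5 and piperonyl butoxide rows then need 272 and 279 per group one-sided (below 333), or 345 and 354 two-sided (above 333).

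**The case against.** The sponsor's case has real force on several points.

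*The exposure size was built on cockroach allergen.* Sample size overviews says so, and the summary gives less weight to the other papers because they lacked repeated measurements, had wide variance estimates and studied narrower groups. That explains the choice of 832, and the target is met. It does not make the pesticide requirement met, and the closing sentence drops the limitation.

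*The 1.5 µg/m³ row is not the formaldehyde target.* This stands. The text before Table 9 relies on a 9.8 µg/m³ difference with at least 37 homes per group, so this row is only the smallest of three scenarios.

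*Table 9 ignores the repeated visits.* This also stands in part. VOCs and pesticides are measured at four visits. Step 4 shows that borrowing the cockroach correlation would bring both rows within 333 one-sided, with power of about 87% and 86%, but not two-sided, with about 79% and 78%. The protocol neither makes this argument nor states a correlation for these analytes.

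A reader might infer more than the documents support:

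- That piperonyl butoxide clearly fails even at full enrolment, since 418 exceeds 416. The gap is two homes, and with the printed design effect of 3.6 the requirement is 415.7. The shortfall that matters is the one after loss.
- That the study is too small for exposures generally. Cockroach allergen and the two larger formaldehyde rows contradict that.
- That 72% is the power the study will have. It is the power of a single-measurement, one-sided comparison.
- That the piperonyl butoxide result converts to a detectable difference in ng/m³ for this study. The source figures are air concentrations; here pesticides are taken by kitchen floor wipe and log-transformed.

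**Conclusion.** The point holds for two rows of Table 9. Compared with about 333 retained homes per group, the plan's own table asks for 418 (piperonyl butoxide) and 408 (formaldehyde 1.5 µg/m³), so the unrestricted adequacy statements conflict with it. Piperonyl butoxide carries most of the weight, because it is the only pesticide calculation. The stated 80% becomes about 72% and 73% one-sided, or 60% and 61% two-sided.

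These figures assume one measurement per home, D = 3.62, equal groups, 20% loss in each group, and the SDs taken from the protocol's two source studies. Two-sided alpha widens the shortfall; a justified repeated-measures correlation narrows it and may close it. Adequacy for cockroach allergen rests on the one-sided z: two-sided, the same formula needs 421 per group. This is a wrong sample-size statement, not a reason to enlarge the study.

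**What to change.** In Sample size overviews, the summary for environmental exposures and the summary for asthma outcomes, limit the adequacy statement to cockroach allergen and formaldehyde differences of at least 3.5 µg/m³, and stop describing the size as conservative for the other rows. Then add, for example:

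> After 20% loss about 333 homes per group are expected. On the basis of Table 9 (one measurement per home, design effect 3.62), this gives about 72% power for the piperonyl butoxide row and 73% for a formaldehyde difference of 1.5 µg/m³ with one-sided alpha 0.05 (about 60% and 61% two-sided), and 80% power from about 0.37 SD one-sided (0.41 SD two-sided).

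Alternatively, recompute Table 9 with the planned repeated visits, a stated and justified correlation for VOCs and pesticides, and a stated sidedness, and apply the 20% loss. If two-sided testing is chosen, recheck the cockroach allergen figure as well. Either way, correct the piperonyl butoxide label to the difference actually used, and do not present an air concentration as this study's detectable pesticide difference.

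The cost is a wording change and a less favourable stated figure. No extra homes or visits are needed.
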